5.1.2.1 Dose Modifications

Dose modification is not permitted in this study for any patient.

5.1.2.2 Treatment Interruption

GDC-8264 treatment may be temporarily suspended in patients who experience toxicity considered to be related to GDC-8264. If GDC-8264 has been withheld for > 14 days because of toxicity, the patient should be discontinued from GDC-8264, unless resumption of treatment is recommended by the investigator after discussion with the MAGIC Principal Investigator and the Medical Monitor.

GDC-8264 treatment may be suspended for reasons other than toxicity (e.g., surgical procedures) in consultation with the MAGIC Principal Investigator and the Medical Monitor. The investigator should consult with the MAGIC Principal Investigator and the Medical Monitor to determine an acceptable length of treatment interruption.

5.1.2.3 Management Guidelines

Guidelines for management of specific adverse events are outlined in Table 7. These guidelines are intended to inform rather than supersede an investigator's clinical judgment and assessment of the benefit–risk balance when managing individual cases.

Event	Action to Be Taken								
Hematologic toxicity									
ANC ≤500/μL (0.5 × 10 ⁹ /L) for 3 days	 Continue GDC-8264 and monitor ANC. If ANC remains ≤ 500/μL (0.5 × 10⁹/L) after 3 days, withhold GDC-8264. Monitor ANC and resume GDC-8264 when ANC > 500/μL (0.5 × 10⁹/L). If not resolved in ≤ 14 days while withholding GDC-8264, permanently discontinue GDC-8264. Note that growth factor use is permitted. 								
Platelet count < 10,000/μL (100 × 10 ⁹ /L) for 7 days	 Continue GDC-8264 and monitor platelet count. If platelet count remains < 10,000/µL (100 × 10⁹/L) after 7 days, withhold GDC-8264. If platelet count sustainable at > 10,000/µL (100 × 10⁹/L) (with transfusions, if necessary), resume GDC-8264. If not resolved in ≤ 14 days while withholding GDC-8264, permanently discontinue GDC-8264. Note that transfusions are permitted. 								
Hepatic events									
Total bilirubin, ALT, or AST increased, and cause is not clearly attributable to aGVHD or other transplant-related complication (e.g., veno-occlusive disease)	 For patients with normal bilirubin, ALT, and AST values at screening: Withhold GDC-8264 for any Grade ≥ 3 increase. If not resolved in ≤ 14 days, permanently discontinue GDC-8264. For patients with elevated bilirubin, ALT, and AST values at screening: If any values > 3 × baseline, withhold GDC-8264 until values resolve to baseline. If not resolved in ≤ 14 days, permanently discontinue GDC-8264. 								

Table 7Guidelines for Management of Patients Who Experience Adverse
Events

aGVHD = acute graft-versus-host disease; PK = pharmacokinetic; QTcF = QT interval corrected through use of Fridericia's formula; ULN = upper limit of normal.

Table 7Guidelines for Management of Patients Who Experience Adverse
Events (cont.)

Event	Action to Be Taken
Seizure	
Any grade	 Immediately withhold GDC-8264 and report event as an adverse event of special interest (see Section 5.2.3). Obtain PK sample as soon as possible. Evaluate event and if not confirmed as seizure, resume GDC-8264. If event confirmed as seizure, permanently discontinue GDC-8264.
ECG abnormalities	
 Any one of the following: Torsades de pointes Sustained (at least two ECG measurements > 30 minutes apart) QTcF that is > 500 ms and > 60 ms longer than the baseline value (i.e., last value prior to initiation of study treatment) Sustained absolute QTcF that is > 515 ms (at least two ECG measurements > 30 minutes apart) New ECG finding of clinical concern 	 Withhold GDC-8264. For torsades de pointes, permanently discontinue GDC-8264. For sustained QTcF events or all other ECG findings of clinical concern, permanently discontinue GDC-8264 when there is no clear alternative cause. If there is a clear alternative cause, GDC-8264 may be resumed at investigator's discretion following consultation with the MAGIC Principal Investigator and the Medical Monitor, provided abnormalities have resolved and patient is appropriately monitored. Contact the MAGIC Principal Investigator and the Medical Monitor as soon as possible. Obtain PK sample if not already scheduled for that timepoint. Initiate standard-of-care treatment at investigator's discretion. Management of sustained QTcF prolongation should include close monitoring, with ECGs repeated at least hourly until two successive ECGs show resolution of the findings, correction of any electrolyte abnormalities, and possible discontinuation of other concomitant medications that are known to prolong the QT interval. Evaluate patient for potential concurrent risk factors (e.g., electrolyte abnormalities, concomitant medications known to prolong the QT interval, severe bradycardia). Consult with cardiologist or electrophysiologist to confirm ECG changes and ascertain the likelihood of drug-induced arrhythmia versus background occurrence of arrhythmias, as it is not uncommon to record arrhythmias such as non-sustained ventricular tachycardia, supraventricular tachycardia, pauses, or atrial fibrillation in healthy volunteers receiving placebo during

aGVHD = acute graft-versus-host disease; PK = pharmacokinetic; QTcF = QT interval corrected through use of Fridericia's formula; ULN = upper limit of normal.

Table 7Guidelines for Management of Patients Who Experience Adverse
Events (cont.)

GDC-8264-related toxicity not described above								
Grade 3 laboratory or non-laboratory abnormality attributable to GDC-8624	•	Withhold GDC-8264. Resume GDC-8264 only after the toxicity has resolved to Grade 1 or better.						
	•	If no improvement to Grade 2 or better in \leq 14 days while withholding GDC-8264, permanently discontinue GDC-8264.						
Grade 4 laboratory or non-laboratory abnormality attributable to GDC-8624 that is not clearly attributable to aGVHD or other transplant-related complication	•	Immediately withhold GDC-8264. If improvement to Grade 2 or better, resume GDC-8264. If no improvement to Grade 2 or better in ≤ 14 days while withholding GDC-8264, permanently discontinue GDC-8264.						

aGVHD = acute graft-versus-host disease; PK = pharmacokinetic; QTcF = QT interval corrected through use of Fridericia's formula; ULN = upper limit of normal.

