5.3.5.6 Abnormal Liver Function Tests

The finding of an elevated ALT or AST (>3×baseline value) in combination with either an elevated total bilirubin (>2×ULN) or clinical jaundice in the absence of cholestasis or other causes of hyperbilirubinemia is considered to be an indicator of severe liver injury (as defined by Hy's Law). Therefore, investigators must report as an adverse event the occurrence of either of the following:

- Treatment-emergent ALT or AST > 3 × baseline value in combination with total bilirubin > 2 × ULN (of which ≥ 35% is direct bilirubin)
- Treatment-emergent ALT or AST > 3 × baseline value in combination with clinical jaundice

The most appropriate diagnosis or (if a diagnosis cannot be established) the abnormal laboratory values should be recorded on the adverse event eCRF (see Section 5.3.5.1) and reported to the Sponsor immediately (i.e., no more than 24 hours after learning of the event), either as a serious adverse event or an adverse event of special interest (see Section 5.4.2).

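### In the readable Table 7, a Hy's Law case can stay below the only hepatic withhold trigger when ALT and AST were normal at screening

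*Combined protocol and SAP*

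**What the plan says.** Section 5.3.5.6 defines the pattern it labels Hy's Law in two ways. One is ALT or AST above 3 × baseline "in combination with total bilirubin > 2 × ULN (of which ≥ 35% is direct bilirubin"). The other is the same ALT/AST rise with clinical jaundice, for which no bilirubin figure is given. In the absence of cholestasis or another cause of hyperbilirubinemia, the finding "is considered to be an indicator of severe liver injury". The section requires reporting within 24 hours as a serious adverse event or an adverse event of special interest (AESI; Section 5.2.3 lists it as one). It states no action on the drug.

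The hepatic row of Table 7 (Section 5.1.2.3) applies when bilirubin, ALT or AST rises and the "cause is not clearly attributable to aGVHD or other transplant-related complication". It has two branches:

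- "For patients with normal bilirubin, ALT, and AST values at screening": "Withhold GDC-8264 for any Grade ≥ 3 increase".
- "For patients with elevated bilirubin, ALT, and AST values at screening": "If any values > 3 × baseline, withhold GDC-8264 until values resolve to baseline".

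In both, failure to resolve within 14 days means permanent discontinuation. Neither branch combines ALT/AST with bilirubin, and neither refers to Section 5.3.5.6. Of the table as a whole, the protocol says "These guidelines are intended to inform rather than supersede" the investigator's judgment.

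**The concern.** The protocol names a laboratory pattern as a marker of severe liver injury, and Section 5.3.4 presumes an event related unless another cause is shown. Yet in patients who start with normal liver tests, the readable drug action is tied to the grade of a single test and not to the pattern. In the same table, seizure (also an AESI) has an immediate withhold and a permanent stop if confirmed. Sustained QTcF prolongation has a withhold, then a stop unless there is a clear alternative cause.

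The setting adds weight. This is the first study of the drug in aGVHD (Section 3.3.4). Dosing may last 56 days, against 14 days in the multiple-dose study described in Section 1.2.2. Dose reduction is not allowed (Section 5.1.2.1), so withholding or stopping is the only drug action available. About 40 patients at about 20 sites is 40/20 = 2 per site, so the same case could be handled differently from one site to the next.

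**Working it through.** The plan gives no figure to reproduce; this is a check of rule logic.

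**Inputs.** The Hy's Law limits come from Section 5.3.5.6 and the withhold rules from the Table 7 hepatic row. Section 5.3.3 names CTCAE v5.0 for grading, but its ALT, AST and bilirubin limits are not printed, so they are assumptions here and are varied.

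**Notation, in multiples of ULN.** b = ALT (or AST) at entry, with b ≤ 1; A = ALT (or AST) on treatment; T = total bilirubin on treatment; LA and LB = the values above which Grade 3 starts for ALT/AST and bilirubin.

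**1. All three tests normal at entry.**

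- Laboratory definition met: A > 3b and T > 2. I also require A > 1, since the section speaks of an elevated value.
- Withhold rule not met: A ≤ LA and T ≤ LB.
- Gap: max(1, 3b) < A ≤ LA and 2 < T ≤ LB.

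Example with LA = 5 and LB = 3: b = 0.5, A = 3.5, T = 2.6. Then 3.5 > 3 × 0.5 = 1.5 and 2.6 > 2, so the definition is met. But 3.5 ≤ 5 and 2.6 ≤ 3, so nothing triggers a withhold.

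ALT/AST band left uncovered (× ULN):

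| Entry value b | LA = 3 | LA = 5 | LA = 8 |
|---|---|---|---|
| 0.5 | 1.5–3 | 1.5–5 | 1.5–8 |
| 0.75 | 2.25–3 | 2.25–5 | 2.25–8 |
| 1 | none | 3–5 | 3–8 |

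Bilirubin band left uncovered (× ULN):

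| LB = 2 | LB = 2.5 | LB = 3 | LB = 5 |
|---|---|---|---|
| none | 2–2.5 | 2–3 | 2–5 |

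Both bands must be open. Apart from the corner case b = 1 with LA = 3, the laboratory gap closes only when LB is 2 or lower. The jaundice limb carries no bilirubin figure, so the bilirubin limit alone does not close it.

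**2. All three tests raised at entry.** The trigger is any value above 3 × baseline. Every Section 5.3.5.6 case has ALT or AST above 3 × baseline, so none escapes.

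**3. Some tests normal, some raised.** These patients are eligible: liver aGVHD of any stage qualifies (Section 4.1.1), Appendix 4 stages the liver on bilirubin alone, and the bilirubin and ALT/AST exclusions in Section 4.1.2 are separate, each with an aGVHD exception. Three tests give 2³ = 8 entry patterns. Taken word for word, 1 + 1 = 2 match a branch and 6 match neither. Read test by test (a normal test follows the Grade 3 rule, a raised test the 3 × baseline rule), all 8 have a rule.

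On that reading, a test that starts normal keeps the gap. With entry ALT 0.8, on-treatment ALT 3.0 and bilirubin steady at 2.5: 3.0 > 2.4 and 2.5 > 2, yet 3.0 ≤ 5 and 2.5 ≤ 3 × 2.5 = 7.5. Here the bilirubin has not moved, so this is not a convincing new liver signal. That matters for how the fix is worded.

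**4. Overlap with liver aGVHD.** At an assumed ULN of 1.0 to 1.2 mg/dL, bilirubin of 2–3 × ULN is 2.0–3.0 to 2.4–3.6 mg/dL. Appendix 4 places those values in liver Stages 1–2. Some cases in the band will be attributed to aGVHD and so fall outside the row.

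**The case against.** **The last row of Table 7 may catch these cases.** It tells the site to withhold for Grade 3 toxicity attributed to the drug. An investigator could record a liver-injury diagnosis, grade it as severe and presume it related. That route exists, but it is not reliable: the row is for toxicity not covered earlier in the table, it starts at Grade 3, and it depends on both grading and attribution.

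**Other safeguards exist.** Medical Monitors can be reached at all times (Section 5.4.1), the sponsor evaluates such events promptly (Section 5.7), treatment may be suspended for related toxicity (Section 5.1.2.2), and it must stop if the investigator or sponsor judges safety to be at risk (Section 4.6.1). All of this is true, and all of it is case by case.

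**Part of the text is redacted.** Section 3.1.2 and one bullet in the Section 4.6.1 stopping list cannot be read. A hepatic rule could sit there, so the point is limited to the readable text. Table 7's hepatic row itself is intact, and seizure appears both there and in Section 4.6.1, so a rule elsewhere would be no reason to leave the row silent.

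**The contrast with other rows is not absolute.** QTcF allows discretionary restart when there is a clear alternative cause. Seizure is a named potential risk and liver injury is not among the readable ones. The healthy-subject study showed no clinically significant drug-related laboratory findings. These points lower the urgency but do not supply the missing line.

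**Stronger readings to avoid.** A reader might infer that sites are told to keep dosing below Grade 3. They are not: the table is silent there and defers to judgment. A reader might also infer that six of eight entry patterns have no rule. That counts logical patterns, not patients, and the test-by-test reading resolves it, so it is a wording point.

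**Conclusion.** The point holds in limited form. In the readable protocol, a patient whose ALT/AST was normal at screening can meet the protocol's own Hy's Law definition without reaching a hepatic withhold trigger, which leaves the drug action to judgment. Patients with all three tests raised are covered.

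The width of the gap rests on assumed grading limits. At 5 × ULN for ALT/AST and 3 × ULN for bilirubin, and with all three tests normal at entry, it spans ALT/AST from 1.5–5 (entry value 0.5) to 3–5 (entry value 1) × ULN with bilirubin 2–3 × ULN. The laboratory part disappears if Grade 3 bilirubin starts at or below 2 × ULN. The documents support no estimate of how many patients would be affected. This does not show that the whole plan lacks a liver stopping rule, because part of the text is redacted. It is a cheap safety improvement that should be made.

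**What to change.** In the existing hepatic row, keeping its scope (cause not clearly aGVHD or another transplant complication), add one line for all patients:

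- **Trigger:** ALT or AST > 3 × baseline and above ULN, with either total bilirubin > 2 × ULN (≥ 35% direct) that has risen from its screening value, or new clinical jaundice (Section 5.3.5.6).
- **Action:** withhold GDC-8264, report as a serious adverse event or AESI, and evaluate the cause.
- **Restart:** only if a clear alternative cause, which may be aGVHD, is established after consultation with the MAGIC Principal Investigator and the Medical Monitor; otherwise discontinue permanently.

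Both qualifiers are needed. With entry ALT 0.3 × ULN, 3 × baseline is 0.9 × ULN, still within normal; and a patient who enters with raised bilirubin from liver aGVHD may already exceed 2 × ULN. Without them, a trivial ALT change could force a withhold.

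Also state that the two existing branches apply test by test, and cross-reference Section 5.3.5.6 to Table 7. If a redacted section already holds such a rule, align Table 7 with it.

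Cost: one line, one phrase and one cross-reference in the next amendment. ALT, AST, total and direct bilirubin are already in the chemistry panel (Section 4.5.9). The downside is some dose interruptions during work-up, including in patients whose liver changes prove to be aGVHD; the documents give no basis for a number. The Table 7 preamble would still leave room for the investigator's judgment.

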5.2 SAFETY PARAMETERS AND DEFINITIONS

Safety assessments will consist of monitoring and recording adverse events, including serious adverse events and adverse events of special interest, performing protocol-specified safety laboratory assessments, measuring protocol-specified vital signs, and conducting other protocol-specified tests that are deemed critical to the safety evaluation of the study.

Certain types of events require immediate reporting to the Sponsor, as outlined in Section 5.4.

5.2.1 Adverse Events

According to the ICH guideline for Good Clinical Practice, an adverse event is any untoward medical occurrence in a clinical investigation subject administered a pharmaceutical product, regardless of causal attribution. An adverse event can therefore be any of the following:

- Any unfavorable and unintended sign (including an abnormal laboratory finding), symptom, or disease temporally associated with the use of a medicinal product, whether or not considered related to the medicinal product
- Any new disease or exacerbation of an existing disease (a worsening in the character, frequency, or severity of a known condition) (see Sections 5.3.5.8 and 5.3.5.9 for more information)
- Recurrence of an intermittent medical condition (e.g., headache) not present at baseline

- Any deterioration in a laboratory value or other clinical test (e.g., ECG, X-ray) that is associated with symptoms or leads to a change in study treatment or concomitant treatment or discontinuation from GDC-8264 (see Section 5.3.5.4 for more information)
- Adverse events that are related to a protocol-mandated intervention, including those that occur prior to assignment of study treatment (e.g., screening invasive procedures such as biopsies)

5.2.2 Serious Adverse Events (Immediately Reportable to the Sponsor)

A serious adverse event is any adverse event that meets any of the following criteria:

- Is fatal (i.e., the adverse event actually causes or leads to death)
- Is life threatening (i.e., the adverse event, in the view of the investigator, places the patient at immediate risk of death)

This does not include any adverse event that, had it occurred in a more severe form or was allowed to continue, might have caused death.

- Requires or prolongs inpatient hospitalization (see Section 5.3.5.10)
- Results in persistent or significant disability/incapacity (i.e., the adverse event results in substantial disruption of the patient's ability to conduct normal life functions)
- Is a congenital anomaly/birth defect in a neonate/infant born to a mother exposed to GDC-8264
- Is a significant medical event in the investigator's judgment (e.g., may jeopardize the patient or may require medical/surgical intervention to prevent one of the outcomes listed above)

The terms "severe" and "serious" are not synonymous. Severity refers to the intensity of an adverse event (e.g., rated as mild, moderate, or severe, or according to National Cancer Institute Common Terminology Criteria for Adverse Events [NCI CTCAE]; see Section 5.3.3); the event itself may be of relatively minor medical significance (such as severe headache without any further findings).

Severity and seriousness need to be independently assessed for each adverse event recorded on the eCRF.

Serious adverse events are required to be reported by the investigator to the Sponsor immediately (i.e., no more than 24 hours after learning of the event; see Section 5.4.2 for reporting instructions).

5.2.3 Adverse Events of Special Interest (Immediately Reportable to the Sponsor)

Adverse events of special interest are required to be reported by the investigator to the Sponsor immediately (i.e., no more than 24 hours after learning of the event; see Section 5.4.2 for reporting instructions). Adverse events of special interest for this study are as follows:

- Cases of potential drug-induced liver injury that include an elevated ALT or AST in combination with either an elevated bilirubin or clinical jaundice, as defined by Hy's Law (see Section 5.3.5.6)
- Suspected transmission of an infectious agent by GDC-8264, as defined below

Any organism, virus, or infectious particle (e.g., prion protein transmitting transmissible spongiform encephalopathy), pathogenic or non-pathogenic, is considered an infectious agent. A transmission of an infectious agent may be suspected from clinical symptoms or laboratory findings that indicate an infection in a patient exposed to a medicinal product. This term applies only when a contamination of the GDC-8264 is suspected.

- Seizure, any grade
- Grade ≥3 syncope

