4.1.2 Exclusion Criteria

Patients who meet any of the following criteria will be excluded from study entry:

- Evidence of relapsed, progressing, or persistent malignancy, or treatment for relapse after transplant, or requirement for rapid immune suppression withdrawal as preemergent treatment of early malignancy relapse
- Prior receipt of more than one allogeneic HSCT
- Prior receipt of solid organ transplantation that are target organs for aGVHD (e.g., liver transplant)
- Prior systemic treatment for aGVHD, except for the standard-of-care corticosteroid treatment initiated as part of this trial (see Section 4.3.2.2)

Topical skin corticosteroid treatment and non-absorbable oral corticosteroid treatment for GI aGVHD are permissible.

- Diagnosis of chronic GVHD or overlap syndrome
- Uncontrolled active infection (i.e., progressive symptoms related to infection despite treatment, or persistently positive blood cultures despite treatment, or any other evidence of severe sepsis)

Persistent fever without signs or symptoms will not be interpreted as an uncontrolled active infection.

In the setting of a pandemic or epidemic, screening for active infections should be considered according to local or institutional guidelines or guidelines of applicable professional societies (e.g., American Society of Clinical Oncology [ASCO] or European Society for Medical Oncology [ESMO]).

- Severe organ dysfunction (e.g., acute liver failure, renal failure requiring dialysis, ventilator support, or vasopressor therapy)
- Direct bilirubin >2 mg/dL within 3 days prior to initiation of GDC-8264 unless the elevation is due to Gilbert syndrome or aGVHD
- ALT/SGPT and AST/SGOT > 5 × the upper limit of normal (ULN) within prior to initiation of GDC-8264, unless due to aGVHD

GDC-8264—Genentech, Inc. 49/Protocol GA43861, Version 4

- Creatinine clearance or estimated glomerular filtration rate < 30 mL/min as calculated by institutional practice (e.g., Cockcroft-Gault equation, CKD-EPI equation)
- Treatment with an investigational small molecule therapy within drug elimination half-lives, whichever is longer, prior to initiation of GDC-8264

An investigational therapy is defined as a drug that has not been approved or authorized by the U.S. Food and Drug Administration for any use.

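### The liver AESI scales ALT and AST to baseline alone, so a normal value can meet its enzyme limb while a large second rise after recovery may not

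*Combined protocol and SAP*

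**What the plan says.** Section 5.2.3 gives no multiple for the enzyme. It speaks of "an elevated ALT or AST in combination with either an elevated bilirubin or clinical jaundice" and defers to Section 5.3.5.6.

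Section 5.3.5.6 opens with "The finding of an elevated ALT or AST (>3×baseline value) in combination with either an elevated total bilirubin (>2×ULN) or clinical jaundice", limited to cases without cholestasis or another explanation for the raised bilirubin. Two reporting criteria follow: "Treatment-emergent ALT or AST > 3 × baseline value in combination with total bilirubin > 2 × ULN" (at least 35% of it direct) and "Treatment-emergent ALT or AST > 3 × baseline value in combination with clinical jaundice". They do not repeat the limitation. In all three places the enzyme is compared with baseline only; just the bilirubin is tied to ULN.

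Section 4.1.2 excludes patients with ALT and AST above 5 × ULN, but with an exemption: "prior to initiation of GDC-8264, unless due to aGVHD". Five times ULN is therefore not a ceiling.

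Section 5.3.5.6 does not define baseline. Table 1 defines it as the last value before the first dose, in a footnote attached to the biomarker endpoints, and Table 7 attaches a similar definition to QTcF. Nothing resets it during the study.

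Table 7 (Section 5.1.2.3) does separate patients by screening values. With normal values it uses a grade; with elevated values it says "If any values > 3 × baseline, withhold GDC-8264 until values resolve to baseline".

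AESIs are reportable within 24 hours (Sections 5.2.3 and 5.4). Section 6.4 tabulates them with patients grouped by treatment received.

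**The concern.** An enzyme called elevated in one section is defined in another by a multiple that takes no account of the normal range. The mismatch works in both directions. A patient with a low-normal baseline can meet the limb without an elevated enzyme. A patient with a high baseline needs a very high value, and keeps needing it after the liver has recovered.

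Raised baselines are to be expected here, because liver involvement alone is a route into the trial (Section 4.1.1, Stage 1–4 liver). Liver staging starts at a bilirubin of 2 mg/dL (Appendix 4), and the bilirubin limb has no comparison with baseline. Depending on the local ULN, some patients may be at or near that limb on Day 1. For them the enzyme limb does most of the discriminating.

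At stake are 24-hour liver reporting and a table by dose. Safety is a co-primary objective and the trial is meant to choose a dose. With about 20 patients per cohort, one case gained or lost moves a cohort's proportion by 1/20 = 5 percentage points.

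**Working it through.** The plan gives no derived figure on this point, so there is nothing to reproduce. The check is direct arithmetic.

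**Inputs.** Multiplier 3 (Section 5.3.5.6); entry level 5 × ULN, higher if due to aGVHD (Section 4.1.2); baseline fixed at the last pre-dose value (the natural reading of Tables 1 and 7). The documents give no ULN in U/L; 40 is assumed, with a range of 30 to 55.

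**Trigger in ULN units** = 3 × (baseline / ULN).

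| Baseline (× ULN) | Enzyme must exceed (× ULN) |
|---|---|
| 0.20 | 0.60 |
| 0.25 | 0.75 |
| 0.30 | 0.90 |
| 1/3 | 1.00 |
| 0.50 | 1.50 |
| 1 | 3 |
| 3 | 9 |
| 5 | 15 |
| 8 (possible if due to aGVHD) | 24 |

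**Low baseline.** A value in the normal range can qualify only if baseline is below ULN/3. That is 40/3 = 13.3 U/L, or 10.0 to 18.3 U/L over the assumed ULN range. Example: 3 × 12 = 36, so 37 U/L meets the limb while below 40.

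**How common such baselines are** is unknown. If baseline ALT were log-normal, the share below 13.3 U/L is Φ[(ln 13.3 − ln median)/log-SD].
- Log-SD 0.5: 27% at median 18 U/L, 16% at 22, 7% at 28.
- Log-SD 0.3: about 16% at median 18, 0.7% at 28.

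All medians and SDs are assumptions. These are shares of baselines, not event rates.

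**High baseline.** 3 × 5 = 15 × ULN, which is 600 U/L at ULN 40 (450 to 825 over the range). This applies enzyme by enzyme: a patient with ALT at 5 × and AST at 1.5 × ULN qualifies once AST exceeds 3 × 1.5 = 4.5 × ULN.

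**After recovery.** If the enzyme that entered at 5 × ULN falls to 1 × ULN, it must then rise more than 15/1 = 15-fold. A rise to 10 × ULN with jaundice fails, because 10 < 15.

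**The same cases under the proposed definition**, with values in ULN units for the raised-baseline cases:
- Baseline 12 U/L: must exceed both 36 and 40, so 37 no longer qualifies.
- Baseline 20 U/L: must exceed both 60 and 40, so the trigger stays at 60.
- Entry 5, lowest value 1: reference = max(1, min(5, 1)) = 1 and trigger = 3, so 10 qualifies.
- Entry 5, no recovery: reference 5 and trigger 15, unchanged.

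**The case against.** **The limb is not the event.** A reader might infer that a normal ALT makes an AESI by itself. It does not: bilirubin above 2 × ULN (at least 35% direct) or jaundice is also required, and Section 5.2.3 is confined to potential drug-induced injury. This stands.

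**The rule is ALT or AST.** A reader might infer that any patient entering with an enzyme at 5 × ULN needs 15 × ULN to qualify at all. The documents support this only for that enzyme. This stands.

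**Missed cases have other routes.** A marked rise that is symptomatic, treated or clinically significant is an adverse event (Section 5.3.5.4). If serious, it carries the same 24-hour deadline (Sections 5.2.2 and 5.4). Section 6.4 also has a laboratory shift table. This largely stands, so what is certain to be lost is the AESI label. The routes depend on judgment, however. Section 5.3.5.9 keeps clear aGVHD worsening out of adverse event reporting, although it sends doubtful cases to it, and a second enzyme rise in a patient with liver aGVHD at entry invites that attribution.

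**A multiple of baseline is reasonable when the disease itself raises liver tests**, and Table 7 uses the same multiple for elevated screening values. This stands for a stable raised baseline. It does not answer the case where the enzyme has normalised.

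**Baseline is not defined in Section 5.3.5.6**, so a fixed reference is an inference. True, but no text supports any other reading, and the gap needs closing anyway.

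**A uniform limit of 3 × ULN would lose sensitivity.** At baseline 20 U/L and ULN 40 the trigger would move from above 60 to above 120 U/L in the first study in patients with aGVHD. This stands, and is why the fix does not require it.

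**Conclusion.** The concern holds for the enzyme limb. Sections 5.2.3 and 5.3.5.6 do not agree on what elevated means when baseline is below ULN/3. Without a reset rule, an enzyme that entered at 5 × ULN and recovered must exceed 15 × ULN to count again. The AESI table in Section 6.4 therefore captures potential liver injury inconsistently across baseline levels.

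Two stronger conclusions might be drawn and are not supported. One is that the table does not measure liver injury at either dose: that does not follow from one limb of a two-part criterion with an either-enzyme rule. The other is that 7–27% of patients would be wrongly counted. That range is an assumed share of baselines below ULN/3 at log-SD 0.5. It includes neither the chance of a more than threefold rise nor the bilirubin or jaundice condition.

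The multiples of ULN follow from the protocol's own figures, given a fixed pre-dose baseline. The U/L values rest on the assumed ULN. How many patients are affected cannot be derived from the documents.

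**What to change.** For reporting and tabulation only, in Section 5.3.5.6:

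1. Define baseline as the last value before the first dose of GDC-8264.
2. Keep the factor of 3, and require the qualifying ALT or AST also to be above ULN.
3. Where baseline is raised, use as reference the lower of baseline and the lowest on-study value before the rise, never below ULN. Apply this enzyme by enzyme.

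Use the same definition for the Section 6.4 AESI table and state it in the Data Analysis Plan. The sponsor should reconcile Sections 5.2.3 and 5.3.5.6 and the hepatic rows of Table 7, so that any remaining difference between the reporting definition and the management table is deliberate. No treatment rule is proposed.

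Whether patients with normal baselines should move to more than 3 × ULN is a sensitivity trade-off for the sponsor.

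**Cost.** ALT, AST and bilirubin are already collected (Section 4.5.9, Appendix 1). The site instruction becomes slightly longer. Some extra reports will come from liver aGVHD flares: an enzyme entering at 10 × ULN, falling to 1 × and returning to 3.1 × would meet the limb (3 × 1 = 3) while still below its entry value.
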